#### VII. STATISTICAL ANALYSIS

The sample size for this study was determined using outcomes from available peer-reviewed literature, anticipated improvements in MR reduction at the conclusion of the procedure, at the time of the hospital dismissal and at 30 days and one year. Specifically the percentage of subjects that demonstrate MR reduction from severe to </+ moderate at the conclusion of the procedure and at 30 days. These data will be used to assess the safety and performance of the device when used on a human subject. These data will be used to assess initial safety and performance of the Harpoon Medical TSD-5, and are not designed to test a statistical hypothesis, and therefore a formal sample size has not been calculated. All data will be captured on an intent-to-treat basis. Data will be reported as descriptive statistics.

# VIII. RISKS AND DISCOMFORTS

There are risks associated by our protocol. The Harpoon Medical TSD-5 device received CE Mark in December 2017. The study uses minimally invasive surgical techniques to repair/replace cords in a human heart. The discomforts we predict are equivalent to what is expected from similar operative procedures (i.e., localized pain, discomfort at the incision site(s)). Should the Harpoon Mitral Valve Repair System not perform as designed, conventional open-heart procedures will be used to facilitate the repair of the mitral valve.

# IX. POTENTIAL BENFITS

The Harpoon Medical TSD-5 will provide many significant advantages over current surgical interventions including: 1) a small minimally invasive incision, 2) no sternotomy, 3) no cardiopulmonary bypass, 4) no aortic manipulation, 5) a direct path to the valve plane, 6) performed on a beating heart, 7) real-time TEE-guided chordal length adjustment and 8) less complicated procedure that is teachable and adoptable. The only intracardiac implant is an ePTFE suture which has a 25+ year history of safety in mitral valve repair procedures.

Importantly, the Harpoon approach will not compromise subsequent traditional open-heart mitral valve repair or replacement procedures

# X. MONITORING AND QUALITY ASSURANCE

The clinical trial site(s) will be monitored in accordance with policies at Harpoon Medical, Inc. and those federal regulations that pertain to clinical research; namely, 21 CFR Parts 50, and 56; and others as applicable.

All SAEs (serious adverse events) and device deficiencies (reported by Investigators or identified by Safety) will be adjudicated by an independent Clinical Endpoint Committee (CEC) through the 36 month follow-up, based on relevant source documents provided from the investigational sites.

The CEC will verify SAE criteria and code. For all confirmed SAEs, CEC will also conduct a causality assessment in regards to the investigational Harpoon device and the index procedure. All adjudication activities are managed by Sponsor's Safety team according to the CEC Charter.

#### **CLINCAL ENDPOINT COMMITTEE**

A Clinical Endpoint Committee (CEC) is responsible for adjudicating all SAEs including device deficiencies which may lead to SAE through the 36 month follow-up visit. In addition, all confirmed SAEs are assessed in regards to relationship to the Harpoon device and Index procedure.

The Sponsor's Safety Department manages all CEC preparation activities according to an approved CEC Charter.

Adjudicated data is used for a final analysis. If event is not adjudicated, site reported data is used.

# a. Appendix A: DATA COLLECTION SCHEDULE

General Assessment	Screening Baseline	Surgery Date	Post-Op	30 Days (30-40 days)	6 Month +/- 30 d	12 Month +/- 30 d	18 Month +/- 30 d	24 Month +/- 30 d	30 Month +/- 30 d	36 Month +/- 30 d	48 Month +/- 30 d	60 Month +/- 30 d
Informed Consent*	X											
Release of Medical Information												
	Х											
Screening Log & Registration	х											
Medical History	X			Х	Х	Х	X	Х	Х	Х	Х	X
Medications	X	X	Х	X	Х	Х	Х	Х	Х	Х	Х	X
Physical Exam	X		Х	X	Х	Х	Х	Х	Х	Х	Х	Х
Laboratory Assessment	х			х								
Eligibility Criteria	X											
Screening Outcome	х											

\*An additional Informed Consent Form will be signed by the subject(s) to reflect the additional follow-up required by this protocol amendment

Cardiac Assessment	Screening Baseline	Surgery Date	Post-Op	30 Days (30-40 days)	6 Month +/- 30 d	12 Month +/- 30 d	18 Month +/- 30 d	24 Month +/- 30 d	30 Month +/- 30 d	36 Month +/- 30 d	48 Month +/- 30 d	60 Month +/- 30 d
Chest X-Ray	X											
NYHA Heart Failure Class	X		X	х	Х	Х	Х	Х	Х	Х	Х	X
6-minute walk test	х					Х						
ECG	X		Х	X								
TTE	X		X	X	Х	Х	Х	Х	Х	Х	X	X
TEE***	X	Х										
Diagnostic Left Heart Cath or Clinical Standard of Care	х											
euroScORE	X											
Pulmonary Function Testing (if	х											
Quality of Life Assessment [SF-36]	х					х						

\*\*\* TEE: may be required if the TTE of the heart cannot adequately evaluate the device

## RETROSPECTIVE COLLECTION OF DATA

Protocol Version 04 extends the patient follow-up to include visits at 48 and 60 months. Protocol Version 03 had introduced additional follow-up visits at 18, 30 and 36 months. These protocols allow retrospective collection of data on any scheduled or unscheduled visits for subjects who participated in the EFS or CE Mark trials (if the subject came back to the hospitals) before

Version: HMFIM -1000-PL-04, 07 August 2019 Page 13 of 15

Versions 03 or 04 are approved by the Ethic Committee (EC) and Competent Authority (CA). Once Protocol Version 04 has been approved by relevant EC and CA, subjects will be contacted and asked to consent to the additional visits and have their data collected. Patients who exited from the trial at 36 months as scheduled per protocol Version 03 will be contacted and requested to continue their follow-up up to 60 months as scheduled by Protocol Version 04.

Two different versions of information letters (informed consent form) will be sent depending on patient status (already exited or not). Each patient will have to sign this letter (informed consent form) to approve collection of additional data.

Version: HMFIM -1000-PL-04, 07 August 2019 Page 14 of 15

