# III. STUDY OBJECTIVES

The purpose of this study is to evaluate the safety and performance of the Harpoon Medical TSD-5. The data collected from this trial was used to support the design of the study to support CE Mark of the TSD-5 Device. The Harpoon Medical device received CE Mark in December of 2017. Enrollment in this trial was completed as of November 2017. Follow-ups range from 12 to 36 months. The purpose of this amendment is to increase the frequency of follow-up and to extend the follow-up to 5 years post-implant.

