#### Safety Goals:

**Primary Safety Endpoints**: Procedure freedom from Serious Adverse Events (SAEs) during the ePTFE implantation procedure, at discharge, and at 30 days follow-up shall be tracked and recorded.

**Secondary Safety Endpoints** Freedom from Serious Adverse Events (SAEs) at 6 months, 12 months, 18 months, 24 months, 30 months, and 36 months follow-up shall be tracked and recorded.

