### V. SUBJECT ENROLLMENT

This is a prospective, nonrandomized, single-centered European study designed single arm study to demonstrate the performance and safety of the Harpoon Medical TSD-5 in Subjects with degenerative mitral regurgitation. A maximum of fifty (50) subjects will be enrolled. The estimated enrollment period is 24 months, and all subjects shall be followed for 30 days, 6 months, 12 months, 18 months, 24 months, 30 months, 36 months, 48 months and 60 months after ePTFE implantation in accordance with the Schedule of Clinical Investigations (see below).

Subject withdrawal from the study: A withdrawal refers to a Subject who is determined to be inactive in the study due to physician discretion, Subject choice (withdrawal of consent), and loss to follow-up or Subject death. Final status will be reported on all Subjects as per the informed consent. Three documented phone calls and a registered/certified letter will be used to assure that there is minimal loss to follow-up. If these efforts to contact the Subject are unsuccessful, the Subject will be considered lost to follow-up.

Pre-procedure/baseline evaluations: All Subjects enrolled in the study will undergo transthoracic echocardiography and transesophageal echocardiography prior to surgery. These are routine preoperative studies for Subjects undergoing heart valve surgery.

Physical Assessment: All study Subjects will undergo a comprehensive history and physical examination. Once enrolled, a physical assessment must be completed within 30 days of the procedure and recorded on a Case Report Form (CRF). In addition to a physical examination and a comprehensive history, the physical assessment will include:

- Vital signs, 12-lead ECG, Laboratory assessment (including WBC count; Hemoglobin; hematocrit; platelet count; creatinine Level, Total Albumin, Total Bilirubin; INR; BNP, NTproBNP) and a chest radiograph (X-Ray)
- A serum pregnancy test for females with childbearing potential (age < 50 years) will be completed within 14 days prior to the procedure.
- As per the standard of care for valve surgery, any subject with symptoms of coronary artery disease and all subjects age >/= 45 years without risk factors shall undergo preoperative diagnostic left heart catheterization ("LHC").
- · Pulmonary Function Tests, when clinically indicated
- 6 Minute Walk test

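### Do retrospective visits and the gap between month-36 exit and re-consent need their own analysis rules?

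*Combined protocol and SAP*

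**What the plan says.** The retrospective-collection section of Appendix A explains that Version 03 added visits at 18, 30 and 36 months and Version 04 added 48 and 60 months. For the period before those versions were approved, it admits data from "any scheduled or unscheduled visits for subjects who participated in the EFS or CE Mark trials (if the subject came back to the hospitals) before" that approval. On the extension it says: "Patients who exited from the trial at 36 months as scheduled per protocol Version 03 will be contacted and requested to continue" follow-up to month 60. It adds: "Each patient will have to sign this letter (informed consent form) to approve collection of additional data".

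Other sections bear on the point:

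- Section V counts death as a form of withdrawal and states: "Final status will be reported on all Subjects as per the informed consent".
- Section VI (Subject follow-up) and the Appendix A schedule give every visit from 6 to 60 months a window of plus or minus 30 days.
- Section III ends the secondary safety goal at month 36: "Freedom from Serious Adverse Events (SAEs) at 6 months, 12 months, 18 months, 24 months, 30 months, and 36 months follow-up". The secondary performance goal lists the same visits.
- Section VII plans intent-to-treat capture and descriptive statistics. It tests no hypothesis and has no rule for missing data, censoring or late entry.
- Section X ends committee adjudication at the 36-month visit.

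**The concern.** Two filters act on the late data. A retrospective assessment exists only if the subject came back, and subjects who return unprompted may differ in mitral regurgitation (MR) from those who stay away, in either direction. After a scheduled month-36 exit, new data need the subject's own signature. Someone who died before being contacted cannot sign, while a survivor who signs might be credited with event-free time over the same interval. If that happened, late mortality would look too low.

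At stake are the descriptive MR and serious adverse event (SAE) results at 18, 30 and 36 months, and the 48- and 60-month follow-up for which Version 04 was written.

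There is also a question of scope. Appendix A speaks of subjects from the EFS or CE Mark trials. Section III presents the CE Mark study as a separate one ("The data collected from this trial was used to support the design of the study to support CE Mark"), and Section V describes a single-centre study.

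**Working it through.** The plan gives no figure to reproduce: it calculates no sample size and reports no counts of deaths, exits or re-consents. What can be checked is how large the gap could be and which results it reaches.

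**Inputs from the protocol.** Section V: "A maximum of fifty (50) subjects will be enrolled. The estimated enrollment period is 24 months". Section III: "Enrollment in this trial was completed as of November 2017. Follow-ups range from 12 to 36 months". Version 04 is dated 7 August 2019.

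**Assumptions.** All 50 subjects enrolled, with even accrual over 24 months ending on 1 or 30 November 2017. Approval follows the version date by 0, 90 or 180 days. Annual mortality is 1 to 3%.

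**Step 1: subjects past month 36.** The first implant falls in November 2015, so that subject reached month 36 in November 2018. Let E be the months from then to approval. Number past month 36 = 50 × E/24; mean gap = E/2; gap person-years = number × mean gap/12; share = person-years/(50 × 2).

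| Lag | E (months) | Past month 36 | Mean gap (months) | Gap person-years | Share of 100 |
|---|---|---|---|---|---|
| 0 | 8.2–9.2 | 17–19 | 4.1–4.6 | 6–7 | 6–7% |
| 90 days | 11.2–12.1 | 23–25 | 5.6–6.1 | 11–13 | 11–13% |
| 180 days | 14.1–15.1 | 29–31 | 7.1–7.6 | 17–20 | 17–20% |

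These are upper figures, because deaths and reoperations leave earlier. With no lag, accrual over 18 or 30 months would give about 8 or 25 subjects instead.

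**Step 2: expected deaths in the gap.** Person-years × annual rate: 6 × 0.01 = 0.06 at the low end and 20 × 0.03 = 0.6 at the high end. A 12-month lag would give about 42 subjects with a mean gap of 10.1 months, so 42.2 × 10.1/12 = 35.5 person-years and 0.36 to 1.07 deaths. The expected number is therefore below one unless approval took about a year or mortality was higher than assumed.

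**Step 3: effect of one unrecorded death.** If 45 of 50 are truly alive, survival is 90.0%. Dropping one death gives 45/49 = 91.8%, a shift of 1.8 points. The exact 95% interval for 45/50 runs from 78.2% to 96.7%.

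**Step 4: retrospective visits.** The share of subjects whose window had closed before approval is (months from first implant to approval − (visit month + 1))/24, held between 0 and 1. The Version 03 approval date is not given, so three dates are assumed.

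| Version 03 approval | Month 18 | Month 30 | Month 36 |
|---|---|---|---|
| January 2018 | 25–29% | 0% | 0% |
| November 2018 | 69–73% | 19–23% | 0% |
| August 2019 | 100% | 55–59% | 30–34% |

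These shares count closed windows. They do not count missing or selected visits, and they measure no bias.

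**Step 5: the two upper figures cannot both hold.** A subject can exit on schedule at month 36 under Version 03 only if that version was in force. If approval came as late as August 2019, the 30–34% whose month-36 window had closed (15 to 17 of 50) could not have exited that way. That leaves about 2 of the 17 to 19 in Step 1.

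**Step 6: is the understatement in the plan?** Missing the gap deaths while crediting the gap time would understate a constant death rate after month 36 by 6 to 20%, the share column above. That needs a person-time death rate. Section VII plans none, and Section III lists no endpoint after month 36.

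**The case for a change.** The strongest case for a change is that nothing in the documents closes either gap. The 30-day windows are set for planned visits and not expressly tied to retrospective ones. The promise of final status is limited by the consent, and a scheduled exit is not among the listed kinds of withdrawal. The sponsor clearly expects such subjects, since separate letters are foreseen for those who have exited. Version 03 introduced the 18-, 30- and 36-month visits, so retrospective filling falls on listed secondary endpoints. Missing data could also outweigh gap deaths: with 10 of 50 subjects lacking late data and 36/40 = 90% observed, the bounds are 36/50 = 72% and 46/50 = 92%.

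Much of this stands as a description. The rules are not written, and the size and direction of any selection are unknown. It does not show that the plan produces a wrong number. The windows are the natural way to place a retrospective assessment. Whether the consent covers vital status cannot be judged, because the consent text is not in the documents reviewed. The missing-data bounds can be read from the visit denominators. The direction of a mortality error is not fixed either: if known deaths are reported while living refusers leave the denominator, the proportion dead is overstated.

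A blanket rule of delayed entry has its own cost. It removes 6 to 20 of at most 100 person-years, widening a rate interval by 1/√0.94 = 1.03 to 1/√0.80 = 1.12. It would also move SAEs and reoperations in the gap out of the rates, although Appendix A allows them to be collected.

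**Conclusion.** No change follows. This is missing detail in a small, single-arm, descriptive study, and analysts can be expected to fill it sensibly. They would place retrospective assessments by the existing windows and mark their source. They would show at each visit how many subjects were seen, dead, reoperated, not re-consented or missing. They would not count the exit-to-re-consent interval as event-free unless vital status is known.

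The primary results stand, and no error rate or power is involved. Any effect is confined to how the descriptive 18-, 30- and 36-month results and the 48- and 60-month follow-up are read. Expected gap deaths are 0.06 to 0.6, assuming 50 subjects, even 24-month accrual, a lag of up to six months and 1 to 3% annual mortality. A longer lag or higher mortality could bring the figure to one or more.

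The mention of the EFS or CE Mark trials is best read as a clerical slip. Sections III and V describe one single-centre study of at most 50 subjects, and that defines whose data belong in it.
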